5.2.3. Worst Itch Numerical Rating Scale (WI-NRS)

The WI-NRS has been developed as a simple, single item to assess the patient-reported severity of this symptom at its highest intensity during the previous 24-hour period. (Newton 2019). The WI-NRS will be determined by the subject's recording of daily assessment of worst itch over the past 24 hours. The scale is from '0 to 10' ("no itch" to "worst itch imaginable" or "worst imaginable itch").

WI-NRS Assessments will be performed according to the Schedule of Visits and Assessments (Section 1.3) starting 7 days prior to the Baseline/Day 1 clinic visit (during the 7 days prior to Baseline/Day 1 the subject will record the WI-NRS value every day).

5.2.4. Dermatology Life Quality Index (DLQI) and Children's Dermatology Life Quality Index (CDLQI)

The DLQI (ages 17+ years) and CDLQI (ages 6-16 years, inclusive) will be performed according to the Schedule of Visits and Assessments (Section 1.3). The DLQI/CDLQI is a simple, self-administered and user-friendly validated questionnaire. The DLQI/CDLQI is designed to measure the health-related quality of life of adult patients suffering from a skin disease. The DLQI/CDLQI consists of 10 questions concerning patients' perception of the impact of skin diseases on different aspects of their health-related quality of life over the last week. Subjects/caregivers will complete the CDLQI/DLQI. Refer to Appendix 8 for the DLQI and Appendix 9 for the CDLQI.

5.2.5. Dermatitis Family Impact Questionnaire (DFI)

This questionnaire measures how much having a child with atopic dermatitis affects the quality of life of other (adult) members of the family. To be completed by parents/guardians/caregivers of subjects ≤ 17 years of age (Appendix 10).

5.3. Other Evaluations

5.3.1. Body Surface Area (BSA)

BSA assessments will be performed according to the Schedule of Visits and Assessments (Section 1.3).

The BSA affected for atopic dermatitis will be determined by the subject's hand method, where the subject's hand (including fingers) surface area is assumed to equal 1% of body surface area (excluding the scalp, palms, soles).

5.3.2. SCORAD ("SCORing Atopic Dermatitis")

SCORAD is a clinical tool for assessing the severity (i.e. extent, intensity) of atopic dermatitis as objectively as possible. It gives approximate weights of 60% to intensity and 20% each to spread (extent) and subjective signs (insomnia, etc.).

See Appendix 11.

5.3.3. Patient-Oriented Eczema Measure (POEM)

The Patient-Oriented Eczema Measure (POEM) is a tool used for monitoring atopic eczema severity. It focuses on the illness as experienced by the patient.

POEM is a 5-point scale measuring the frequency of each of seven AD symptoms (dryness, itching, flaking, cracking, sleep loss, bleeding, and weeping) over the past week scored as occurring "no days" (0), "1 to 2 days" (1), "3 to 4 days" (2), "5 to 6 days" (3) or "every day" (4). Total score ranges from 0–28, with higher score indicating greater symptom impact. See Appendix 12. The self/proxy report questionnaire will be used in this study (for children unable to read and/or understand the POEM questionnaire, the parent/guardian/caregiver will complete the questionnaire).

5.3.4. Pharmacokinetics Assessment

PK draws will be performed according to the Schedule of Visits and Assessments (Section 1.3) for all subjects at all sites:

• A single PK assessment (trough) will be performed in all subjects with a blood sample collected at Week 4/Day 29.

Ensure study medication is not applied in the area where PK will be drawn.

5.3.5. Medical Photography

Photography of AD lesion(s) selected by the Investigator will be performed by all sites at all investigational visits, except Week 2/Day 15. All efforts will be made to de-identify the subjects. Canfield equipment will be used to capture photographs.

Photography should be focused on single lesions or specific body sections (e.g. arm). Body or half body photos should only be taken if necessary. Subjects who are unwilling to participate in the medical photography will be allowed to opt out of this procedure and documented on the informed consent.

Refer to the current Photography Manual for instructions regarding photography.

5.4. Final Study Visit – End of Study

The approximate final study visit will occur at Week 4/Day 29. The procedures performed during this visit are as described in the Schedule of Visits and Assessments (Section 1.3). A 3-day scheduling window is allowed for this visit. Adverse events will be recorded as reported by the participant or and followed to resolution or stabilization (as necessary).

5.5. Early Termination Visit

If a subject is withdrawn or wishes to exit the study, a termination visit will be scheduled. This visit should include the procedures and assessments that would be performed at the Week 4/Day 29 visit.

5.6. Unscheduled Visit

Unscheduled visits may be necessary to repeat testing following abnormal laboratory results, for follow-up of AEs, or for any other reason, as warranted in the judgement of the Investigator.

The following information will be collected for all subjects:

- Concomitant medications/procedures
- AEs

The following information also will be collected:

- vIGA-AD and EASI
- BSA affected with AD

• Local tolerability assessment (by Investigator)

The rules for how to tally vIGA-AD, BSA or other proportions of categorical responses will be described in the Statistical Analysis Plan.

5.7. Adverse Events

5.7.1. Adverse Event Definition

An AE is defined as any untoward medical occurrence associated with the use of a drug in humans, whether or not considered drug related. An AE can therefore be any unfavorable and unintended sign (including an abnormal laboratory finding), symptom, or disease temporally associated with the use of a medicinal (investigational) product, whether or not related to the medicinal (investigational) product.

A treatment emergent adverse event (TEAE) is defined as an AE that started post application of study medication at the Baseline visit or was present at treatment initiation but worsened during treatment, through study completion.

The definition of AEs includes worsening of a pre-existing medical condition. Worsening indicates that the pre-existing medical condition has increased in severity, frequency, and/or duration or has an association with a worse outcome. When recording such events, provide descriptions that the pre-existing condition has changed (eg, worsening hypertension for a subject with pre-existing hypertension). A pre-existing condition that has not worsened during the study or involves an intervention, such as elective cosmetic surgery or a medical procedure while on study, is not considered an AE.

Progression of atopic dermatitis including new or worsening of anticipated clinical signs or symptoms, which are collected as clinical efficacy variables and assessed as unequivocally associated with the disease progression and /or lack of efficacy, should NOT be reported as adverse events unless the disease progression is greater than anticipated in the natural course of the disease.

In general, abnormal laboratory findings without clinical significance (based on the investigator's judgment) are not to be recorded as AEs. However, abnormal laboratory findings that result in new or worsening clinical sequelae, or that require therapy or adjustment in current therapy, are considered AEs. Where applicable, clinical sequelae (not the laboratory abnormality) are to be recorded as the AE.

5.7.2. Serious Adverse Event Definition

The definitions and reporting requirements of the Food and Drug Administration (FDA)/ICH Guidelines for Clinical Safety Data Management, Definitions and Standards for Expedited Reporting, Topic E2A will be adhered to. Statements regarding mandatory reporting of all serious unexpected adverse drug reactions (SUSARs) to Health Canada [as per C.05.014 (1) of the FDR] will be adhered. If any AEs are serious, as defined by ICH Guidelines for Clinical Safety, required procedures will be followed.

An SAE is defined as any AE that, in the view of either the PI or Sponsor, meets at least 1 of the following serious criteria:

- Fatal
- Life-threatening (places the subject at immediate risk of death)
- Requires inpatient hospitalization or prolongation of existing hospitalization
- Results in a persistent or significant incapacity/disability
- Congenital anomaly/birth defect.
- Other important medical events that, based upon appropriate medical judgment, may jeopardize the subject and may require medical or surgical intervention to prevent one of the outcomes listed in the above definition.

Hospitalization does not include the following:

- Rehabilitation facilities, hospice facilities or respite care (e.g. caregiver relief)
- Nursing homes or skilled nursing facilities
- Emergency room visits
- Same day surgeries (as outpatient/same day/ambulatory procedures)
- <24 hour admissions for observation or evaluation

Hospitalization or prolongation of hospitalization in the absence of a precipitating, clinical AE is not in itself an SAE. Examples include:

- Admission for treatment of a preexisting condition that did not worsen
- Hospitalizations for cosmetic elective surgery, social, and/or convenience admissions
- Pre-planned treatments or surgical procedures should be noted in the baseline documentation for the individual subject.
- Diagnostic and therapeutic procedures, such as surgery, should not be reported as AEs; however, the medical condition for which the procedure was performed should be reported if it occurs during the reporting period and meets the definition of an AE. For example, an acute appendicitis that begins during the AE reporting period should be reported as an AE, and the resulting appendectomy should be recorded as treatment of the AE.

Unexpected is defined as an AE that is not listed in the IB or is not listed at the specificity or severity that has been observed; or is not consistent with the risk information described in the general investigational plan or study document.

If a SAE occurs to a subject on this study, contact the Medical Monitor within one business day of knowledge of event.

5.7.3. Suspected Unexpected Serious Adverse Reaction (SUSAR)

SUSAR is defined as a serious adverse reaction, the nature or severity of which is not consistent with the known study treatment information. A serious event or reaction is not defined as a SUSAR when: 'it is serious but expected' or it does not fit the definition of an SAE, whether expected or not.

5.7.4. Safety Review with Subject

At each subsequent clinic visit after the screening visit, subjects will be queried with an open-ended question such as: 'How have you been feeling since your last visit?' Additionally, the study staff will review subject diaries and, if it appears that a potential AE was recorded, study staff will query the subject and determine if an AE occurred.

AEs (whether serious or non-serious) and clinically significant abnormal laboratory test value(s) will be evaluated by the PI and treated and/or followed for up to one month after end of treatment until the symptoms or value(s) return to normal, or acceptable levels, as judged by the Investigator.

Where appropriate, medical test(s) and/or examination(s) will be performed to document resolution of event(s). Outcome may be classified as resolved, improved, unchanged, worse, fatal or unknown (lost to follow-up).

5.7.5. Adverse Event Reporting

The Investigator is responsible for recording all adverse events, observed by the clinic staff or reported by the subject that occur after the first application of investigational product through one month after treatment permanently discontinues. Serious adverse events observed by the clinic staff or reported by the subject after signing the informed consent form will be recorded.

All adverse events that meet the criteria for "serious" (i.e., SAEs) will be reported to the Sponsor via fax or e-mail within 24 hours of becoming aware of the event, whether or not the serious events are deemed drug-related. Reporting should be done by sending the completed SAE form to the following e-mail address (faxing can also be done as a second option in case e-mailing is not possible).

Safety C	Contact Information:	
E-mail:		

All serious event reporting will adhere to ICH E6: Guideline for Good Clinical Practice and ICH E2A: Clinical Safety Data Management: Definitions and Standards for Expedited Reporting. The IRB will be notified of the Alert Reports as per FDA, ICH and the IRB's policies and procedures. The sponsor, or delegate, will be responsible for reporting SAEs to health authorities per local reporting requirements. The Investigator will be responsible for reporting for reporting events to their respective IRBs in accordance to the IRB requirements.

The Investigator will review each adverse event and assess its relationship to Investigational Product (unrelated, unlikely, possibly, probably, likely). Each sign or symptom reported will be graded on the NIH NCI CTCAE toxicity grading scale 5-point severity scale (Grade 1, 2, 3, 4

Confidential

and 5). The date and time of onset, time relationship to drug dosing, duration, and outcome (resolved, improved, unchanged, worse, fatal, or unknown/lost to follow-up) of each event will be noted.

• The relationship of each AE to the Investigational Product will be assessed using the following definitions:

Unrelated	The AE must clearly be caused by the subject's clinical state, or the study procedure/conditions. Definitely not related to drug. Temporal sequence of an AE onset relative to administration of drug not reasonable. Another obvious cause of an AE.
Unlikely	Time sequence is unreasonable. There is another more likely cause for an AE.
Possibly	Corresponds to what is known about the drug. Time sequence is reasonable. Could have been due to another equally, likely cause.
Probably	Is a known effect of the drug. Time sequence from taking drug is reasonable. Ceases on stopping the drug. Cannot be reasonably explained by the known characteristics of the subject's clinical state.
Likely	Is a known effect of the drug (e.g., listed in Physicians' Desk Reference, Compendium of Pharmaceuticals and Specialties, IB). Time sequence from taking drug is reasonable. Event stops upon stopping drug, event returns upon restarting drug.

The following CTCAE toxicity grading scale 5-point severity scale definitions for rating maximum severity will be used:

Grade 1	Mild; asymptomatic or mild symptoms; clinical or diagnostic observations only; intervention not indicated.
Grade 2	Moderate; minimal, local or noninvasive intervention indicated; limiting age- appropriate instrumental activities of daily living.*
Grade 3	Severe or medically significant but not immediately life-threatening; Hospitalization or prolongation of hospitalization indicated; disabling; limiting self-care activities of daily living.**
	Note: An experience may be severe but may not be serious, e.g., severe headache).
Grade 4	Life-threatening consequences; urgent intervention indicated.
Grade 5	Death related to AE.

Note: A semi-colon indicates 'or' within the description of the grade.

- * Instrumental activities of daily living refer to preparing meals, shopping for groceries or clothes, using the telephone, managing money, etc.
- ** Self-care activities of daily living refer to bathing, dressing and undressing, feeding self, using the toilet, taking medications, and not bedridden.

AEs will be coded using the most current MedDRA[®] version available at the start of the study.

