13.1 Adverse Events

Adverse events (AEs) will be coded according to the latest available version of Medical Dictionary for Regulatory Activities (MedDRA) (Version 23.0 or higher).

Treatment emergent adverse events (TEAEs) are defined as any AEs with onset on or after the first study drug application. See Appendix 2 for handling of completely or partially missing dates for AEs. In the case where it is not possible to define an AE as treatment emergent or not, the AE

	STATISTICAL ANALYSIS PLAN, Version 1.0
Protocol Number: ARQ-151-312	Sponsor: Arcutis Biotherapeutics, Inc.

will be classified as treatment emergent. All reported TEAEs will be summarized by treatment group.

Overall summary will be presented, which will include the total number of events, and the number and percentage of subjects who experienced TEAE, TEAE by the strongest relationship, TEAE by the maximum severity, treatment-related TEAE by maximum severity, treatment-emergent serious AE (TESAE), treatment-emergent Non-SAE, TEAE leading to study treatment discontinuation, TEAE leading to study discontinuation, TEAE on an application site, and TEAE leading to death.

The number and percentage of subjects who experience TEAE will be summarized by SOC and PT within SOC. In addition, similar table will be presented by treatment groups for age 6 to 17 years and ≥ 18 years separately. Unless otherwise specified, a subject experiencing the same TEAE multiple times will be counted only once for the corresponding PT. Similarly, if a subject experiences multiple TEAEs within the same SOC, the subject will be counted only once for that SOC. TEAEs will be sorted alphabetically by SOC and within each SOC the PT will be presented by descending frequency in the safety analysis set. A treatment-related TEAE is defined as any TEAE that is assessed by the Investigator as likely, probably, or possibly related to study treatment. TEAE that is assessed as unrelated or unlikely will be defined as not treatment-related. If a subject experiences more than one TEAE within different relationship categories within the same SOC/PT, only the worst case (the strongest relationship) will be reported. TEAE with an unknown relationship will be considered as treatment-related.

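### The causality grades in protocol 5.7.5 build expectedness into relatedness, so a previously unknown reaction has no fitting related grade and treatment-related counts may be understated

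*Protocol*

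**What the plan says.** Protocol 5.7.5 asks the investigator to grade each adverse event as Unrelated, Unlikely, Possibly, Probably or Likely, and defines each grade in a few short sentences. The three upper grades all open with prior knowledge:

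- Possibly: "Corresponds to what is known about the drug. Time sequence is reasonable", followed by a sentence allowing for another cause that is equally likely.
- Probably: "Is a known effect of the drug. Time sequence from taking drug is reasonable", with resolution on stopping and no reasonable explanation in the subject's clinical state.
- Likely: "Is a known effect of the drug (e.g., listed in" reference sources that include the IB), with resolution on stopping and return on restarting.

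The two lower grades rest on timing and other causes. Unlikely reads "Time sequence is unreasonable. There is another more likely cause for an AE". Unrelated begins "The AE must clearly be caused by the subject's clinical state, or the study procedure/conditions".

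SAP 13.1 turns the grades into a two-way split: "A treatment-related TEAE is defined as any TEAE that is assessed by the Investigator as likely, probably, or possibly related to study treatment". Unrelated and Unlikely count as not related. An unknown relationship counts as related.

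Expectedness has its own definitions. In protocol 5.7.2, "Unexpected is defined as an AE that is not listed in the IB"; the sentence goes on to cover events that are listed, but not as specifically or as severely as observed. In protocol 5.7.3, "SUSAR is defined as a serious adverse reaction, the nature or severity of which is not consistent with the known study treatment information".

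**The concern.** Whether a drug caused an event and whether the event was already known are separate questions. Protocol 5.7.2 and 5.7.3 treat the second as its own item, but the scale in 5.7.5 also makes it part of the first. An investigator who sees something new, with convincing timing and no competing explanation, finds a prior-knowledge condition on every grade that counts as related.

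Prior knowledge is thin for part of this population. Protocol 2.3.2 describes the oral safety data as coming mainly from middle-aged and older people who smoke or have smoked. Protocol 2.4.2 says the topical profile looks different from the oral one. The Phase 2 atopic dermatitis trial (2.3.1.5) had 8 adolescents among 136 subjects, and this trial enrols from age 6. At stake is whether the treatment-related summaries can show effects that are not already on record.

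**Working it through.** No formula applies. The check takes defined events through the five definitions, with every sentence in a definition required, and then follows the result into the SAP and the reporting rules.

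**Event A: not previously known, reasonable timing, no other cause, no information on stopping or restarting.**

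| Grade | What blocks it | Fits? |
|---|---|---|
| Unrelated | No clear other cause; timing is reasonable | No |
| Unlikely | Timing is reasonable; no more likely cause | No |
| Possibly | Not part of what is known; no equally likely other cause | No |
| Probably | Not a known effect; resolution on stopping not shown | No |
| Likely | Not a known effect; stopping and restarting not shown | No |

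Result: 0 of 5 grades fit. The event falls into a gap. The scale does not itself send it to the not-related side.

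**Event B: as A, but it resolves on stopping and returns on restarting.** It meets every condition of Likely except the known-effect one. An event that only resolves on stopping meets every condition of Probably except the same one. In both cases prior knowledge alone blocks the grade that the causal evidence supports.

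**Effect of deleting the prior-knowledge conditions.** Event B then fits Likely, and the stopping-only version fits Probably. Event A still fits nothing, because Possibly mentions an equally likely other cause and Probably needs resolution on stopping. Deletion alone therefore does not close the gap.

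**Through the SAP.** If the investigator chooses Unlikely or Unrelated, the event is missing from the treatment-related TEAE summary by maximum severity and counts as not related in the summary by strongest relationship. If the relationship is recorded as unknown, SAP 13.1 counts it as related, but unknown is not among the five grades in 5.7.5. In every case the event stays in the overall TEAE tables by system organ class and preferred term, which are repeated for ages 6 to 17 and for adults.

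**Through the reporting rules.** Protocol 5.7.5 sends every SAE to the sponsor within 24 hours, whatever its relationship to study drug, and commits serious-event reporting to ICH E2A. Neither 5.7.2 nor 5.7.3 refers to the five-grade scale. Nor do the documents describe a separate sponsor assessment of causality. The only causality definitions they supply are therefore the ones that favour known effects, while a SUSAR is a reaction at odds with what is known.

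**Size.** The number of misgraded events cannot be derived. One could assume an incidence for a new reaction and compute expected cases among about 433 active subjects (650 × 2/3). That number would be the same under any causality scale, so it does not measure misgrading.

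**The case against.** The strongest reply is that the sentences under each grade are descriptors to be weighed, not conditions that must all hold. The protocol never says all are required, and the strict reading gives odd results elsewhere: a well-timed event with an obvious other cause would fail both Unrelated and Unlikely, since both mention unreasonable timing. The Possibly wording is also looser than a known effect and can be read as pharmacologically plausible.

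Much of this stands. A reader might infer that a new reaction cannot be rated related at all. The text does not go that far, because an investigator who reads Possibly loosely can use it. But treating the sentences as alternatives does not rescue the scale: reasonable timing appears in all three upper grades, so any well-timed event would meet all three. The loose reading of Possibly also still leaves Probably and Likely tied to a known effect, so a new reaction confirmed by stopping and restarting is held at a grade meant for events with an equally likely other cause.

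A reader might also infer that such an event necessarily leaves the treatment-related tables. It does not follow. The lower grades fit no better, and SAP 13.1 counts an unknown relationship as related. Loss from the tables is possible, not automatic.

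The most tempting inference is that a new reaction can never be a SUSAR, or that expedited reporting is disabled. The documents contradict this. Unexpectedness includes a listed effect at unlisted specificity or severity, so a known effect can be graded related and still be unexpected. The IB is only one of the example sources under Likely, so an effect known from elsewhere can be related and unlisted. All SAEs reach the sponsor regardless of grade, and protocol 5.7.2 separately commits to SUSAR reporting to Health Canada. Protocol 5.9 also calls for contact with the Medical Monitor over conditions the investigator thinks could be drug-related, with no known-effect test.

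**Conclusion.** The concern holds as a definitional fault. Every grade counted as treatment-related carries a prior-knowledge element, and on a literal reading a new, well-timed event without another cause fits none of the five. Treatment-related TEAE counts may therefore understate new reactions by an unknown amount, and the scale is inconsistent in spirit with the SUSAR definition. Detection of new signals through the all-causality tables and the flow of SAEs to the sponsor is intact, which limits the consequence.

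The conclusion rests on two assumptions. The first is that at least some investigators apply the definitions closely; looser use shrinks the effect. The second is that the wording is still in force: the protocol supplied is marked as the original, while SAP section 1 follows Amendment 3. The SAP uses the same five grade names, but it does not reproduce their definitions. The change is worth making because it is cheap, not because a large error has been shown.

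**What to change.** 1. In protocol 5.7.5, remove the known-effect condition from Probably and Likely and the correspondence-with-knowledge condition from Possibly. Grade on time sequence, response to stopping and restarting, and alternative causes.
2. Reword the grades so that a well-timed event without an alternative cause has a related grade even when nothing is known about stopping or restarting.
3. Judge listedness separately, under the existing definition of unexpected in 5.7.2.
4. Confirm whether Amendment 3 keeps the 5.7.5 wording. If it has already been changed, only the query below may be needed, for events graded under the old text.
5. Before database lock, and blinded, ask sites to re-confirm the grade of TEAEs rated Unrelated or Unlikely that have reasonable timing and no recorded alternative cause. Do not select on a stated reason for the grade: 5.7.5 does not list one among the items recorded.

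The cost is a wording change in the protocol and any matching eCRF guidance, plus one query round. The treatment-related count may rise slightly. The efficacy analysis is untouched.
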